## 6.2 IRB Approval and Informed Consent

\*Baseline/eligibility procedures, including informed consent, may occur at any time from consultation until radiation therapy treatment begins.

### **6.3. Accrual Goals and Monitoring**

Patients will be referred by their physician by calling the Clinical Research Coordinator (CRC) in the Radiation Oncology department at the University of Pennsylvania. Patient eligibility will be verified based upon the criteria outlined in Section 4.1. and Section 4.2. After eligibility is established and confirmed, a subject study number will be issued. We anticipate enrollment of four-five patients per month onto this study.

### **6.4. Study Calendar / Schedule**

Event	Baseline/Eligibility	Prior to RT Initiation	Weekly during RT
Informed Consent	X*	X*	
History and Physical	X	X	
Photon and Proton Treatment Planning and/or Baseline MR scan	X	X	
3D/4D CT and/or MR scans (determined by tumor location and treating physician)			X*
Blood Draw (prior to each imaging scan during RT)**		X	X

\* These are research specific procedures. All other procedures are standard of care.

\*\* Only if receiving contrast with imaging).

### **6.5. Pre-Registration /Pre-Treatment**

#### **Baseline/Eligibility**

See Section 5.3 (Subject Recruitment and Screening) and Section 5.1 and 5.2 (Inclusion and Exclusion Criteria).

#### **Radiation Treatment Planning**

The radiation dose will be prescribed at mid-separation on the central ray for two equally weighted beams. For all other beam arrangements, the dose will be prescribed at the center of the target area or at the intersection of central rays of the beams.

Simulation for all fields is required for treatment planning. Patients will undergo simulation with an MR scan and/or CT scan per best clinical practices, and 4D imaging will be employed as indicated, at the discretion of the treating radiation oncologist. The 4D CT will be used to define the target volumes. The gross tumor volume (GTV) will consist of all known sites of disease including the primary tumor and all pathologically enlarged ( $\geq 1$  cm in short axis) positive lymph nodes prior to accounting for respiratory motion. Discontinuous volumes are allowed. In 4D planning CTs, the GTV will be

## **Quantification of Tumor and Organ at Risk (OAR) Volume and Motion Path Changes during Definitive Photon or Proton Beam Radiotherapy**

expanded to create an internal tumor volume (ITV), which will include the GTV and the extent of GTV respiratory movement as defined by the 4D CT. The clinical tumor volume (CTV) and planning target volume (PTV) will be constructed from the GTV by an automatic margining tool supervised and edited by the treating radiation oncologist. The irradiation target volume will be defined by shaped ports with custom-made blocks or multileaf collimation. Portal verification shall be done for all treated fields. Megavoltage equipment is required with minimum peak photon energies of 6 MV. SAD techniques should be used. Each field will be treated every session. Interruptions in therapy should be discussed with the principal investigator but will be instituted at the discretion of the attending radiation oncologist.

Dose calculation should be performed using inhomogeneity corrections to account for differences in tissue density across the thorax. The total dose to gross disease will be 40-80 Gy, depending on the standard of care for using radiotherapy to treat the primary tumor (with or without concurrent chemotherapy) and on the site of the primary tumor. The prescribed total dose and dose per day will be constrained to adjust for the standard normal tissue dose limitations.

## **RADIOTHERAPY PLANNING**

Forward photon and proton beam plans will be generated on the CT simulation data set. These plans will be then be applied to the up to weekly data sets to quantify variance in dose deposition.

**Treatment planning is not routinely changed during the course of radiation therapy. However, if it is found by the treating physician that a significant change has occurred in tumor volume, position or anatomy that render the original plan no longer optimal, then a new treatment plan will be created for the remainder of treatment. Should this occur, the PI will be notified of the treatment changes.**

### **6.6. *On Treatments***

Based on the primary tumor location and the discretion of the treating radiation oncologist, patients will undergo 3D/4D CT Scan (up to weekly) and/or MR Scan (minimum of 3).. The GTV, ITV and critical normal structures will be contoured on each up to weekly/serial scan. The up to weekly/serial GTV volume will be compared to the initial GTV volume to determine changes in tumor volume. Each GTV will be compared to the initial ITV volume to determine what percent of the GTV resides within the initial ITV. This value will be used to evaluate changes in tumor motion. Each ITV will be compared to the initial ITV. The initial photon treatment plan and proton treatment plan will be applied to the new scan. The amount of radiation dose to each GTV, ITV and critical normal structures will be recorded to determine the changes in dose distribution that occur as treatment progresses. **SUBJECTS WILL RECEIVE ALL SCANS IN THE RADIATION ONCOLOGY CLINIC OF THE UNIVERSITY OF PENNSYLVANIA.**

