### **9.3 *Objectives:* To determine changes over time in:**

1. tumor volume variables
2. tumor motion
3. patient anatomy
4. dose distribution to tumor and critical normal organs

**9.4 Endpoints:** To be measured at baseline and then weekly during 7-8 weeks of radiotherapy

1. GTV (gross tumor volume), the volume of the primary tumor visualized on the CT scan
2. ITV (interior tumor volume), the GTV expanded to include interior motion (i.e., breathing or swallowing) such that the tumor resides within the ITV during normal motion
3. CTV (clinical tumor volume), the ITV expanded to include microscopic disease (margins)
4. PTV (planning tumor volume), the CTV expanded by several mm, as determined by radiation dosimetry planning, PTV is considered the ultimate target volume

NOTE the relationship: GTV < ITV < CTV < PTV

5. Dose coverage: at each scan time point, determine the percent of the GTV which resides within the baseline ITV or CTV
5. patient weight and percent weight loss from baseline
6. Radiation dose to critical normal organs based on dose-volume histograms (i.e., 20 Gy to 50% of normal lung tissue)

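### ITV change and ITV dose are required on every on-treatment scan, but the only stated way to build an ITV needs 4D CT, which neither baseline nor follow-up is required to use

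*Combined protocol and SAP*

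**What the plan says.** Section 6.6 leaves the mode of on-treatment imaging open, by tumor location and physician discretion: "patients will undergo 3D/4D CT Scan (up to weekly) and/or MR Scan (minimum of 3"). It then asks for the same contours whatever the mode: "The GTV, ITV and critical normal structures will be contoured on each up to weekly/serial scan". Two uses of the on-treatment ITV follow. "Each ITV will be compared to the initial ITV", and the dose to each ITV is recorded. A third quantity, the percent of each on-treatment GTV lying inside the initial ITV, is named as the measure of motion change.

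The construction of an ITV is given once, in section 6.5 under Radiation Treatment Planning. It applies to 4D planning CTs, where the ITV comprises "the GTV and the extent of GTV respiratory movement as defined by the 4D CT". The same section makes baseline 4D optional: "4D imaging will be employed as indicated, at the discretion of the treating radiation oncologist".

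Section 9.4 lists ITV as an endpoint and describes it as "the GTV expanded to include interior motion (i.e., breathing or swallowing) such that the tumor resides within the ITV during normal motion". That is a concept without a method. Section 9.4 also defines the containment percentage against the baseline ITV or CTV, without saying when each applies. Section 9.5 analyzes percent change from baseline in the volume variables with signed-rank tests (item 1), containment (item 2) and dose to GTV and ITV (item 4). No section links follow-up mode to baseline mode or gives an ITV rule for a static scan.

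**The concern.** A static scan shows the tumor at one point of its path, or blurred over an unknown part of it. The protocol describes no way to read the motion path from a 3D CT or an MR scan. A contourer told to draw an ITV there has two obvious choices: draw it as the GTV, or carry over the baseline motion margin. The first makes the ITV shrink when nothing has changed. The second assumes the answer to the question being asked. The protocol does not choose, so contourers may differ.

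Motion path is in the study title, and tumor motion is part of the primary aim. The error would not behave like noise. Scan mode depends on tumor site and physician, and drawing the ITV as the GTV errs in one direction only, so 30 patients per stratum would not average it out. A signed-rank test could then report a change in scan mode as a change in the tumor.

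The containment percentage has a separate problem of reference. A patient without a 4D baseline has no 4D-derived ITV to contain anything. The option in 9.4 of ITV or CTV then allows different reference volumes in one stratum. This is most likely in the GI stratum, which runs from esophagus to rectum.

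**Working it through.** The plan states no figure on this point, so there is nothing to reproduce. The check is a geometric illustration.

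**Inputs.** Motion h = 0.5 to 1.0 cm: the quiet-breathing range for lung tumors in section 2.0. Tumor diameter 2 to 5 cm (radius r = 1.0 to 2.5 cm): an assumption, as the documents give no tumor sizes. Shape: a sphere moving rigidly along a straight line, also an assumption.

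**Step 1: static ITV drawn as the GTV, no true change.** GTV = (4/3)πr³. ITV = GTV + πr²h. The false ITV loss is

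πr²h / [(4/3)πr³ + πr²h] = h / (h + 4r/3).

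| Diameter | h = 0.5 cm | h = 1.0 cm |
|---|---|---|
| 2 cm | 0.5/1.833 = 27.3% | 1.0/2.333 = 42.9% |
| 3 cm | 0.5/2.5 = 20.0% | 1.0/3.0 = 33.3% |
| 5 cm | 0.5/3.833 = 13.0% | 1.0/4.333 = 23.1% |

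The range is 13% to 43%. Outside that lung range, the 1.8 cm axial motion quoted in section 2.0 for the distal esophagus gives 1.8/(1.8 + 2.0) = 47.4% at 3 cm diameter.

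**Step 2: motion truly changes, GTV does not.** Take r = 1.5 cm, so GTV = 4.5π cm³. The ITV is 5.625π at h = 0.5 cm and 6.75π at h = 1.0 cm.

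| True motion | True ITV change | Margin copied | ITV drawn as GTV |
|---|---|---|---|
| 1.0 to 0.5 cm | 5.625/6.75 − 1 = −16.7% | 0% | 4.5/6.75 − 1 = −33.3% |
| 0.5 to 1.0 cm | 6.75/5.625 − 1 = +20.0% | 0% | 4.5/5.625 − 1 = −20.0% |

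Neither convention recovers the truth, and in the second row drawing the ITV as the GTV reverses the sign. Dose to an ITV drawn either way is dose to the wrong volume.

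**Step 3: percent of GTV inside the initial ITV, static follow-up after a 4D baseline.** This needs the follow-up GTV and the baseline ITV only. An unchanged tumor reads 100% at every breathing phase, so there is no false loss. If the tumor has shifted along the motion axis, let d be the distance by which the imaged sphere passes the end of the baseline path. The share inside is 1 − 3d/(4r) + d³/(16r³). With r = 2 cm and h = 1 cm:

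- True shift 0.5 cm: d = 0 at the near end and the middle of the cycle, giving 100%. At the far end d = 0.5, giving 1 − 0.1875 + 0.001 = 81%.
- True shift 1.0 cm: d = 0, 0.5 and 1.0 at the near end, middle and far end, giving 100%, 81% and 1 − 0.375 + 0.008 = 63%.

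A Monte Carlo overlap calculation gave the same values (100.0%, 81.4% and 63.3%). The measure can be computed, but the same shift reads differently with the phase captured.

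**The case against.** A reader might infer that the protocol's motion measure is also lost on 3D CT or MR scans. The documents do not support that. Sections 6.6, 9.4 and 9.5 all set the on-treatment GTV against a baseline volume, and none uses an on-treatment ITV. After a 4D baseline the measure survives. Restricting it to 4D follow-up would discard usable data, most likely in lung and some GI patients, for whom section 2.0 says 4D planning is often used. What remains is its dependence on phase and, without a 4D baseline, the missing ITV reference.

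A reader might also infer that CTV and PTV inherit the error. That follows from 9.4, which builds them outward from the ITV. Section 6.5 builds them from the GTV. The two definitions conflict, so inheritance cannot be taken as settled.

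Three further points are fair. First, 9.4 defines ITV without naming a scan mode. That rules out saying ITV is defined only from 4D CT, but a definition without a method does not tell a contourer what to draw. Second, a 4D baseline followed by a static scan is permitted but not shown to be common: mode depends partly on tumor site, which is fixed for each patient. Where neither scan is 4D, this false shrinkage does not arise, but the 6.5 construction then gives no ITV at all. Third, the percentages hold only if the ITV is drawn as the GTV, which no passage instructs.

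The study is a descriptive pilot not powered for testing, and its tumor-volume comparison, GTV with GTV, is unaffected. That limits the damage. It does not excuse the gap, because in a descriptive study the measurements are the result.

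**Conclusion.** The concern holds for ITV volume change and for dose to the on-treatment ITV. On any non-4D scan, the protocol requires a quantity that its own construction cannot supply. An ITV drawn as the GTV gives a false loss of about 13% to 43% in an unchanged tumor, under the assumed sphere of 2 to 5 cm diameter and the protocol's 5 to 10 mm lung motion. A copied margin fixes the motion part of the change at zero. For scale only, section 2.0 cites a median GTV reduction of 44.3% at 50 Gy in NSCLC, which is a different quantity.

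The containment percentage stands on static scans after a 4D baseline, subject to breathing phase. Without a 4D baseline it lacks a 4D-derived ITV reference, and 9.4 lets the reference vary within a stratum. How many patients would be affected cannot be estimated from the documents. The point should be corrected because it concerns a stated primary interest of the study and costs little.

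**What to change.** Change the wording of sections 6.6, 9.4 and 9.5 as follows.

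- (a) Derive ITV volume change and on-treatment ITV dose only from pairs with a 4D baseline and a 4D follow-up scan. On 3D CT or MR scans, contour the GTV and normal structures and do not construct an ITV.
- (b) When baseline was 4D, keep the percent of GTV within the initial ITV on all follow-up scans, and report it by scan mode.
- (c) For patients without a 4D baseline, use the baseline CTV as the containment reference. Report these values separately and do not pool them with ITV-referenced values.
- (d) Record scan mode on the CRF, and breathing phase where available.

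The cost is revised text and one or two CRF fields, with no extra scans and no change to treatment. The downside is that fewer patients contribute to the ITV-change and ITV-dose endpoints, including any lung or GI patients with a 4D baseline and non-4D follow-up. The number contributing should be reported with each of these endpoints.

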## Quantification of Tumor and Organ at Risk (OAR) Volume and Motion Path Changes during Definitive Photon or Proton Beam Radiotherapy

### PROTOCOL OVERVIEW

In recent years, conformal techniques have been developed that allow for precise delivery of radiotherapy to the primary tumor and regional lymphatics while minimizing the dose to normal tissues. These approaches are predicated upon precise anatomic localization of the regions to be irradiated. Unfortunately, at present, most conformal treatment delivery approaches do not account for changes in tumor volume, tumor motion or changes in patient anatomy during the time course of definitive radiotherapy. Proton beam radiotherapy can potentially allow for ultra-precise delivery of treatment due to the physical characteristics of the proton beam. Therapeutic proton beam radiotherapy allows for the elimination of exit dose and a significant reduction in the entrance dose to the patient while maximizing dose delivered to the tumor (Figure 1). However, accurate treatment delivery with proton beam radiation is predicated upon precise definition of tumor volume and location. Tumor volume reduction during definitive proton beam radiotherapy has resulted in significant dosing errors, with dose deposition in unintended regions (MDACC PTCOG 47). The purpose of this protocol is to quantify the extent of tumor volume, motion, and anatomic changes that occur during the tumor course of definitive photon beam radiotherapy. As both proton beam and photon beam radiotherapy have nearly identical biological efficacy, the changes observed during photon beam radiotherapy should closely approximate that which would likely be observed during proton beam irradiation.

**Quantification of Tumor and Organ at Risk (OAR) Volume and Motion Path Changes during Definitive Photon or Proton Beam Radiotherapy**

Figure 1: Comparison of Dose Deposition between Photon and Proton Beam Radiotherapy

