**Secondary Aims**

To utilize the data generated from the photon or proton beam patients to simulate and estimate the degree of error if tumor volume, tumor motion path and patient anatomy changes are unaccounted for during treatment with proton beam radiotherapy by generating simulated serial proton plans with this data.

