### 3.0 SPECIFIC AIMS/OBJECTIVES

**Specific Aim 1:** To estimate the degree of tumor volume, tumor motion and patient anatomy change during treatment with photon beam radiotherapy.

- 1a. To estimate the degree and impact of tumor volume change during the course of definitive photon radiotherapy treatment in lung cancers, head and neck cancers, gastrointestinal cancers (including but not limited to colorectal and rectal cancers) and gynecological cancers.
- 1b. To estimate the degree and impact of tumor motion (anatomic location) change during the course of definitive photon radiotherapy treatment in lung cancers, head and neck cancers, gastrointestinal cancers (including but not limited to colorectal and rectal cancers and gynecological cancers).
- 1c. To estimate the degree and impact of changes in patient anatomy during the course of definitive photon radiotherapy treatment in head and neck and upper gastrointestinal cancers.

Hypothesis: Tumor volume and motion will change over the course of radiation treatment in patients with lung cancers, head and neck cancers, gastrointestinal cancers (including but not limited to colorectal and rectal cancers) and gynecological cancers. The weight loss experienced by patients with upper gastrointestinal and head and neck cancers will have a significant impact on their anatomy. These changes will alter the dose distribution of the photon beam treatment plans, possibly limiting radiation dose delivery to the target volumes and increasing radiation toxicity to surrounding critical structures.

**Specific Aim 2:** To estimate the error if tumor volume, tumor motion and patient anatomy change during treatment with proton beam radiotherapy.

- 2a. To generate simulated proton beam plans using serial CT or MR imaging obtained from either photon or proton beam patients to estimate the dosimetric error if these changes are unaccounted for during proton treatment.

[figure not shown]
Hypothesis: The changes in tumor volume and motion and patient anatomy will have a greater effect on appropriate dose distribution in plans using proton beam therapy compared to photon beam therapy given the need for more accurate target delineation in proton beam therapy.

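### Tumor motion has three meanings in the plan and is scored by the percent of GTV inside the initial ITV, which cannot isolate a change in motion

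*Combined protocol and SAP*

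**What the plan says.** Section 9.3 lists tumor motion as one of four objectives. The term has more than one meaning:

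- **Title:** "Motion Path Changes during Definitive Photon or Proton Beam Radiotherapy". The Secondary Aims likewise refer to "tumor motion path and patient anatomy changes are unaccounted for during treatment with proton beam radiotherapy".
- **Section 3.0, Aim 1b:** "To estimate the degree and impact of tumor motion (anatomic location) change during the course of definitive photon radiotherapy treatment". Here motion means position.
- **Section 6.6:** "Each GTV will be compared to the initial ITV volume to determine what percent of the GTV resides within the initial ITV", followed by "This value will be used to evaluate changes in tumor motion".
- **Section 9.4:** the same percentage is listed as dose coverage, and the reference may be the baseline ITV or the baseline CTV.
- **Section 9.5 item 2 (Tumor Motion):** summarises that percentage over time. It also plans a paired signed-rank test of baseline ITV or CTV variables against later GTV.

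Section 6.5 (Radiation Treatment Planning) defines the GTV as the primary tumor and "positive lymph nodes prior to accounting for respiratory motion". It then builds the ITV by adding the extent of respiratory movement seen on 4D CT. Section 6.6 adds "Each ITV will be compared to the initial ITV" and names no metric for that comparison. Whether on-treatment scans are 3D CT, 4D CT or MR depends on tumor location and the treating physician. No endpoint in 9.4 is a displacement, an amplitude or a path length.

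**The concern.** The study is descriptive (9.2), so its product is the set of quantities it measures. A motion objective needs a variable that changes when motion changes and holds still when it does not.

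The overlap percentage does neither. It rises as the tumor shrinks, falls as the tumor shifts, and depends on which respiratory phase the GTV was drawn on, which the plan does not state. A stable or rising percentage could be reported as little change in motion when the path had lengthened. A falling one could reflect a position shift with an unchanged path. Section 9.5 item 6 then looks for the earliest scan at which most patients show clinically important changes in tumor volume or location, so location needs its own clean measure.

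**Working it through.** The plan states no figure for motion, so there is none to reproduce. The check is a simple geometric model.

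**Inputs**
- GTV reduction 44.3%: section 2.0, lung, median at 50 Gy.
- Baseline excursion 5-10 mm: section 2.0, lung, quiet breathing. Main case A = 10 mm.
- Assumed, because the documents give no tumor size: spherical GTV of radius r = 20 mm, moving along a straight line.
- Assumed for illustration: excursion doubles to 20 mm, lengthening equally at both ends.

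**Volumes**
- GTV = (4/3)πr³ and ITV = (4/3)πr³ + πr²A.
- Baseline: GTV = 33.5 cm³, ITV = 46.1 cm³.
- After 44.3% shrinkage, r₁ = 20 × (1 − 0.443)^(1/3) = 16.46 mm.

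**Overlap with the initial ITV**

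The initial path runs from −5 to +5 mm. With doubled excursion the end-phase GTV is centred at +10 mm, so d = 5 mm beyond the end of the initial path. The part inside is the overlap of two spheres of radii R = 20 and r₁ at distance d:

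π(R + r₁ − d)² × [d² + 2d(R + r₁) − 3(R − r₁)²] / (12d)

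| Situation | Percent of GTV inside initial ITV |
|---|---|
| Excursion doubled, mid-phase GTV, with or without shrinkage | 100% |
| Excursion doubled, end-phase GTV, no shrinkage | 81.3% |
| Excursion doubled, end-phase GTV, 44.3% shrinkage | 97.7% |
| Excursion unchanged, rigid 10 mm shift, mid-phase GTV, 44.3% shrinkage | 97.7% |

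The last two rows agree because both place the GTV centre 10 mm from the middle of the initial path. The percentage cannot tell a shift from a longer path, and shrinkage alone lifts it from 81% to 98%.

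**Is ITV volume a substitute?**
- r = 20 mm, 44.3% shrinkage: ITV falls 41.0% with excursion unchanged (27.2 against 46.1 cm³) and 22.6% with excursion doubled (35.7 against 46.1 cm³).
- Diameters 2-8 cm, baseline excursion 5-10 mm, excursion doubled, 44.3% shrinkage: the fall is 10.1% (2 cm, 10 mm) to 37.5% (8 cm, 5 mm).
- The sign depends on the shrinkage. In the 20 mm/10 mm case with doubled excursion, ITV rises 5.2% at 20% shrinkage and breaks even at 24.6%.

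ITV volume contains the excursion but is confounded with tumor size.

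**The signed-rank comparison in 9.5 item 2**

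Section 9.4 states GTV < ITV < CTV. If volumes are compared, a difference exists even when nothing has changed. In the model, an unchanged GTV of 33.5 cm³ against its own baseline ITV of 46.1 cm³ is already 27% smaller (33.5/46.1 = 0.727).

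**The case against.** Aim 1b equates motion with location, and the overlap is a reasonable way to ask whether the tumor is still where the plan expected it. For coverage that stands, and the overlap should be kept for it. As a location measure it still gives 98% for a 10 mm shift of the shrunken tumor.

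A reader might infer several stronger points that the documents do not support:

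- *The plan would report motion with the wrong sign through ITV volume.* No section says ITV volume change will be read as motion. Section 9.5 places the volume variables under tumor volume, and 6.6 names no metric for comparing ITVs.
- *Nothing in the study captures excursion.* An ITV contoured on 4D CT includes it, and both GTV and ITV are contoured on each scan. In the model ITV/GTV = 1 + 3A/(4r), which is 1.375 at baseline, 1.46 after 44.3% shrinkage with unchanged excursion, and 1.91 with doubled excursion. The information is in the images, but a metric for it is not in the plan. The ratio also moves with shrinkage alone, so it is not a clean substitute.
- *The title and secondary aim concern respiratory motion specifically.* They say motion path. The respiratory reading comes from section 2.0 and the ITV definition, and 9.4 also counts swallowing.
- *Overlap swings widely with the end phase contoured.* Values of 63% (no shrinkage) and 78% (44.3% shrinkage) at end-inhale, against 100% at end-exhale, require all the lengthening to occur at the inhale end. Under symmetric lengthening the two end phases agree.
- *The proton error aim is damaged.* Sections 6.5 and 6.6 apply the initial plans to each new scan and record dose directly. The overlap score is not an input.

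The study is also a descriptive pilot in which 4D imaging is discretionary, so an excursion endpoint will not exist for everyone. That limits the scope of the remedy and leaves the need for a definition.

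**Conclusion.** The concern holds in limited form. Tumor motion is a listed objective without a single meaning, and the measure assigned to it cannot isolate motion. In the worked case a doubled excursion scores 100%, 98% or 81% depending on phase and shrinkage, and a rigid shift of the shrunken tumor scores the same 98%. These values rest on an assumed spherical GTV of radius 20 mm, a straight path and symmetric lengthening. Doubling is illustrative, and no passage predicts it. Other sizes change the values but do not give the percentage the ability to separate the causes. The point about the signed-rank test is conditional on its being a comparison of volumes, which 9.5 leaves unclear. This should be corrected before analysis. It does not affect the dose calculations.

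**What to change.** In 9.4 and 9.5, replace the single motion entry with two named endpoints:

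1. **Location:** GTV centroid displacement from the planning scan, in mm, on one stated phase. Keep the overlap percentage as a coverage measure only, with one stated reference volume.
2. **Motion path:** for patients with serial 4D scans, peak-to-peak GTV centroid excursion in mm on each 4D scan, and its change from the planning 4D CT.

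Use these in 9.5 item 2 in place of the signed-rank comparison of baseline ITV or CTV with later GTV. State that ITV volume change is not interpreted as motion change. Align the wording of Aim 1b, the secondary aim and 6.6 with the two terms.

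The cost is a short text edit and some extra contouring on scans already acquired. The path endpoint exists only for patients with serial 4D imaging, so the number contributing in each stratum should be reported. Centroid location can still move if a tumor shrinks unevenly. Excursion compares the same tumor across phases of one scan and largely avoids that problem.
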